9.1.1. Endpoints

- 1 The proportion of targeted HCPs who acknowledge receiving each of the RM tools.
- 2 The proportion of targeted HCPs who acknowledge reading and utilizing the tools.
- 3 The proportion of targeted HCPs who responds to correctly to questions about the risks of phototoxicity, SCC of the skin, and hepatic toxicity.
- 4 The proportion of targeted HCPs who provided desirable responses to the practicerelated questions and self-declared behavior with regard to strategies to mitigate the risks.

9.2. Setting

The target population will include all HCPs who were targeted to receive Vfend® aRMM materials within 12 months preceding the survey.

At the time of protocol writing, approximately to HCPs were prescribing/dispensing voriconazole in Saudi Arabia and around of these targeted to receive the RM tools in-person, per Pfizer Inc.'s Distribution List. Given this relatively small pool of HCPs, an empirical sample size of 10 HCPs is proposed.

HCPs recruitment and survey will be conducted by the following process:

- HCPs will be invited to participate in the survey by email and/or phone. An email
 invitation will include a web link directing to a webtool named 'Decipher', where the
 survey questionnaire will be available. In the invitation, the survey background and
 objectives, the contact information for questions will be explained to the HCPs.
 Instructions detailing the survey requirements will be displayed at the start of the
 survey.
- If the HCPs agree to participate in the survey, they can access the survey and the instructions for the web questionnaire by clicking on the email link.
- If the questionnaire is not completed in the first attempt, HCPs will receive a reminder email and/or phone (first reminder) 1 week after the initial invitation.
- If the web questionnare remains incomplete, a second reminder will be sent about 2 weeks after the initial invitation.
- If the questionnaire still remains incomplete, a third (and final) reminder will be sent 3 weeks after the initial invitation.

An HCP will be considered unreachable if he/she has been contacted up to 3 times without an answer. For each recruited HCP, the number of times the HCP is contacted, as well as the date and time when he/she completes the web questionnaire, will be recorded. HCP recruitment will be competitive.

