6. MILESTONES

Milestone	Planned date
Start of data collection	15 November 2024
End of data collection	15 February 2025
Registration in the HMA-EMA Catalogues of RWD Studies	10 November 2024
Final study report	30 June 2025

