9.4.1. Data Collection Process

Eligible HCPs (those HCPs to whom the RM tools were distributed by hand) will receive a letter by E-mail inviting them to participate in the survey. The invitation letter will include: an overview of the rationale for the survey, reminder about the educational materials, the secure URL to be copied and pasted into their browser, and a unique user identifier (ID). The survey data collection will be open until 10 completed surveys are received, up to 60-90 days. The survey start date begins within 12-18 months after initiation of distribution (05 February 2023) of the aRMMs tools in the Saudi Arabia.

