9.5. Study Size

At the time of protocol writing, a total of HCPs (distribution list shared with Saudi Food and Drug Authority [SFDA]) are expected to initiate or manage patients on Vfend®. All HCPs who were targeted to receive the RM tools (per Pfizer Inc.'s Distribution List.) within the 12 months preceding the initiation of the survey will be invited to participate in the survey. Given this relatively small pool of HCPs, an empirical sample size of 10 HCPs is proposed. Data will be collected until 10 completed surveys are obtained or up to a data collection period of 60 to 90 days as a maximum. It is important to note that the final survey sample size will depend on HCPs' willingness to participate in the survey.

An a priori threshold of 80% correct responses per risk question will be used to define the success of the program. However, this criterion will not be used for formal statistical testing. The selection of this threshold for success was regarded as being subjective and not based on prior knowledge, experience, or established scientific criteria.

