Annex 1.1. Abstract

Title

Evaluation of the effectiveness of additional risk minimisation measures (aRMMs) that aim to reduce the risks of phototoxicity, squamous cell carcinoma (SCC) of the skin and hepatic toxicity in patients receiving voriconazole in the Saudi Arabia.

Protocol version and date

Version 1.0 16 August 2024

Name and affiliation of main author

Rationale and Background

Pfizer Saudi Limited will conduct a non-interventional, cross-sectional survey of healthcare professionals (HCPs) to evaluate the effectiveness of the aRMMs being implemented across Saudi Arabia to mitigate the risks of phototoxicity, SCC of the skin and hepatic toxicity in patients prescribed voriconazole (Vfend®), a broad spectrum triazole antifungal agent used to treat or prevent a range of serious fungal infections in both inpatient and outpatient settings.

To ensure that the risks are adequately managed, aRMMs in Saudi Arabia have been implemented since February 2023. The aRMM material distribution has been started on 05-February-2023 and continued until 05-February-2024 to the relevant HCPs who may initiate or manage patients on Vfend[®]. These include an updated voriconazole Summary of Product Characteristics (SPC)¹ (routine) and a new comprehensive education programme at the point of patient care that will educate/remind HCPs about the risks of phototoxicity, SCC of the skin and hepatic toxicity and how to manage them. The details of the Risk Minimisation (RM) tools for the educational programme and how these tools will be implemented across Saudi Arabia are described in the Risk Management Plan (RMP). The RM tools are the HCP Checklist, HCP Question & Answer (Q&A) Brochure and Patient Alert Card. HCPs who the materials are targeting will be invited to participate in the survey. The start of the data collection is intended to be within 18-24 months period from the launch of Vfend[®] in Saudi Arabia to allow physicians time for familiarity and use of the materials before evaluating the effectiveness of Vfend[®] aRMM.

Research Question and Objectives

The overall objective is to evaluate the effectiveness of the aRMMs to mitigate the risks of phototoxicity, SCC of the skin and hepatic toxicity in patients using voriconazole. The

Redacted

evaluation is being conducted in Saudi Arabia where RM tools are being implemented. Specifically, the objectives of the study are to:

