In accordance with the SFDA Guideline on Good Pharmacovigilance Practices Module XVI (Risk minimisation measure: selection of tools and effectiveness indicators 30 January 2023)¹, data collection will begin after initial implementation of a RM programme in Saudi Arabia in February 2023 within 18-24 months), in order to allow the possibility of necessary amendments following the initial distribution of the approved RM tools in Saudi Arabia. This period will allow for the time required for utilization of the tools in Saudi Arabia health care

system. The planned timeline is contingent upon the date of the finalization and distribution of the RM tools within Saudi Arabia and the protocol endorsement by the SFDA.

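### The 12-month limit on when HCPs were targeted for the tools covers only 82 of the 365 distribution days, and it contradicts the protocol's other statements of who is eligible

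*Protocol*

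**What the plan says.** **Who is in the frame.** Section 9.2 states: "The target population will include all HCPs who were targeted to receive Vfend® aRMM materials within 12 months preceding the survey". Section 9.5 makes the limit operational: HCPs targeted "within the 12 months preceding the initiation of the survey will be invited to participate in the survey". The Population and Study Size parts of the abstract (Annex 1.1) repeat both statements.

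**When the tools went out.** Annex 1.1, under its rationale, says: "The aRMM material distribution has been started on 05-February-2023 and continued until 05-February-2024 to the relevant HCPs".

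**When the survey runs.** Section 6 gives "Start of data collection 15 November 2024" and "End of data collection 15 February 2025".

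**How the start relates to distribution.** Section 9.4.1 says: "The survey start date begins within 12-18 months after initiation of distribution (05 February 2023) of the aRMMs tools in the Saudi Arabia". The milestones part of the abstract says "data collection will begin after initial implementation of a RM programme in Saudi Arabia in February 2023 within 18-24 months". The rationale part of the abstract also gives 18-24 months, but counts from the launch of Vfend in Saudi Arabia.

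**Other statements of eligibility.**
- Section 9.4.1 treats as eligible the HCPs who were handed the tools, with no date limit.
- Section 9.1 mentions 12 months once, in a phrase that can be read as applying only to self-reported prescribing.
- Inclusion criterion 2 in Section 9.2.1 and screening question Q2 apply 12 months to treating a patient with voriconazole. No inclusion or exclusion criterion concerns the date of targeting.

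**The concern.** All four endpoints in Section 9.1.1 are proportions of targeted HCPs. The frame therefore fixes what is estimated, who is invited, and who can enter the response-rate denominator in Section 9.7. A look-back on targeting is harmless only if it spans the distribution period. Here distribution ended more than nine months before the survey starts, so a 12-month look-back reaches only the last part of it.

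Two features of the protocol make this hard to accept as intended. First, the abstract delays the survey so that physicians have time to become familiar with the materials and use them. The look-back drops HCPs whose only targeting was 12 to 21 months before the survey, the ones who had most time. Second, Sections 9.2 and 9.5 justify a sample of 10 by the small pool of HCPs. A frame that may reduce that pool further needs a reason, and none is given. The only stated purpose for a 12-month window is the mitigation of recall bias in Section 9.9.2, and that is tied to prescribing or dispensing, not to when the tools arrived.

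The conflicting eligibility statements also mean that two people working from this protocol could draw up different invitation lists.

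**Working it through.** The protocol states no coverage figure of its own, so there is none to reproduce. The check is calendar arithmetic.

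**Inputs**
- Distribution: 05 Feb 2023 to 05 Feb 2024 (Annex 1.1), which is 365 days.
- Survey start: "15 November 2024" (Section 6).
- Look-back: 12 months before survey initiation (Section 9.5).
- Protocol date: 16 Aug 2024 (title page).

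**Step 1: coverage of the distribution period.** Look-back start = survey start minus 12 months = 15 Nov 2023.
- Days outside = 05 Feb 2023 to 15 Nov 2023 = 283; 283 / 365 = 77.5%.
- Days inside = 365 − 283 = 82; 82 / 365 = 22.5%.

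**Step 2: dependence on the start date.** Excluded share of days = (look-back start − 05 Feb 2023) / 365, held between 0 and 1.

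| Survey start | Basis | Look-back start | Days excluded | Share |
|---|---|---|---|---|
| 05 Feb 2024 | 12 months (9.4.1) | 05 Feb 2023 | 0 | 0% |
| 05 Aug 2024 | 18 months (9.4.1 and abstract) | 05 Aug 2023 | 181 | 49.6% |
| 15 Nov 2024 | Section 6 | 15 Nov 2023 | 283 | 77.5% |
| 05 Feb 2025 | 24 months (abstract) | 05 Feb 2024 | 365 | 100% |

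The look-back covers the whole distribution period only if the survey starts at the earliest date that Section 9.4.1 allows.

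**Step 3: from days to HCPs.** The protocol gives no targeting date per HCP, and the list size is not visible in the public text. If every HCP was last targeted on or after 15 Nov 2023, 0% are excluded. If every HCP was targeted only before that date, 100% are. Even targeting over the year, with one contact each, gives about 78%. An HCP targeted more than once could qualify through a later contact.

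**Step 4: the start window.**
- 05 Feb 2023 to 15 Nov 2024 is 649 days; 649 / 30.4375 = 21.3 months. This is outside 12-18 months and inside 18-24.
- 05 Feb 2023 plus 18 months = 05 Aug 2024, which is 11 days before the protocol date. The window in Section 9.4.1 had closed before the protocol was issued.

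**Step 5: the eligibility statements side by side.**

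| Place | Limit on date of targeting | 12 months on voriconazole use |
|---|---|---|
| 9.2; abstract, Population | yes | not stated |
| 9.5; abstract, Study Size | yes, from survey initiation | not stated |
| 9.1; abstract, Study Design | ambiguous | yes |
| 9.4.1 | none | not stated |
| 9.2.1 and Q2 | none | yes |

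**The case against.** The strongest reply is that the exclusion is not settled. Section 9.4.1 would invite everyone given the tools by hand, Section 9.1 can be read as limiting only prescribing, and neither the criteria nor the screening questions ask when an HCP was targeted. On that view the 12 months in Section 9.2 is loose wording for the use criterion. This stands in part: the protocol contradicts itself, and the early recipients cannot be said to be certainly excluded. But Section 9.5 attaches the window to receipt of the tools, anchors it to survey initiation and makes it the rule for invitation. That is more than loose wording.

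Three stronger readings are tempting, and the documents do not support them.
- *About four in five targeted HCPs are excluded.* A reader might infer this from the 77.5%, but that figure counts days. It carries over to HCPs only under an even-targeting assumption that nothing in the protocol supports. Nor is it shown that 10 completed surveys become unreachable.
- *The remaining HCPs give results biased in a known direction.* Those retained were targeted between about 9.3 months (05 Feb 2024 to 15 Nov 2024: 284 / 30.4375) and 12 months before the start. Questions Q14 to Q16 ask about use over the past 12 months, so most of that period is covered. A shorter recall interval and a shorter time to use the tools may also pull in opposite directions. Neither sign nor size is established.
- *Counted from 15 February 2025, the window contains no distribution at all.* The arithmetic is right, but Section 9.5 counts from survey initiation, so this is not a fair reading of the rule.

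It is also true that this is a small descriptive survey without formal testing, and that Section 9.9.2 admits selection and representativeness limits. Those limits concern who chooses to respond. They do not cover HCPs left off the invitation list by the protocol's own rule.

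**Conclusion.** The point holds as a defect in how the frame is defined. If Sections 9.2 and 9.5 are followed as written with the planned start, HCPs whose only targeting fell before 15 November 2023 are outside the target population for all four endpoints and are not invited. That period is 283 of the 365 distribution days (77.5%). The figure rests on the distribution dates in the abstract, the planned start in Section 6 and the anchor in Section 9.5. The number of HCPs affected and the effect on the estimates cannot be determined from the protocol.

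The start-window conflict is a separate error that stands on its own dates. It bears on the first point only in that the excluded share of days depends on when the survey starts.

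**What to change.** **Frame.** In Sections 9.2 and 9.5 and in the Population and Study Size parts of the abstract, define the frame as all HCPs on the distribution list targeted at any time from 05 February 2023 to 05 February 2024. Reword Section 9.1, the Study Design part of the abstract, and the eligibility statement in Section 9.4.1 to match. Keep the 12-month look-back for voriconazole use only, as in inclusion criterion 2 and Q2. The share of distribution days excluded then falls from 77.5% to 0%.

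**Start window.** In Section 9.4.1 replace 12-18 months with 18-24 months after the start of tool distribution on 05 February 2023. Use that same anchor in both places in the abstract, which at present count from the launch of Vfend in one and from implementation in February 2023 in the other.

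**Cost.** These are wording changes. The distribution list already exists, and neither the questionnaire nor the sample target changes. More invitations may be needed, depending on how many HCPs were targeted early. The changes should be in place before the invitation list is drawn up.

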9.2.1. Inclusion criteria

Participants/ HCPs must meet all of the following criteria to be eligible for inclusion in the survey:

- 1. Willing/consent to participate in this self-administered survey.
- 2. Involved in the treatment of at least 1 patient with voriconazole within the last 12 months.

Evidence of an electronically signed and dated informed consent document indicating that the participant/ HCP has been informed of all pertinent aspects of the study.

9.2.2. Exclusion criteria

Participants/ HCPs meeting any of the following criteria will not be included in the survey:

- 1. Employed in full-time research or hospital administration (i.e., non-practising physicians).
- 2. Employment by Pfizer Inc or any research organization/vendor contracted by Pfizer to administer the survey.

9.3. Variables

Screening questions

- Consent to participate.
- Whether the HCP managed patient(s) treated with voriconazole during the last 12 months period preceding the survey.
- Employment by Pfizer or any research organization/vendor contracted by Pfizer to administer the survey.
- Participation in qualitative research of the VFEND (voriconazole) Risk Minimisation materials.

HCP demographics and medical background

- 1. Location
- 2. Primary medical specialty
- 3. Length of professional practice as a HCP

HCP knowledge on voriconazole toxicities:

- 1. Knowledge testing for specific risks associated with voriconazole treatment
- 2. Knowledge of treatment discontinuation recommendations and dealing with toxicities

RM tools receipt

- 1. Acknowledge receiving Q&A brochure
- 2. Acknowledge receiving HCP checklist
- 3. Acknowledge receiving Patient alert card

RM tools reading

- 1. Acknowledge reading Q&A brochure
- 2. Acknowledge reading HCP checklist
- 3. Acknowledge reading Patient alert card

RM tools utilization

- 1. Frequency of using HCP checklist, Q&A brochure, and Patient alert card
- 2. Ranking the usefulness of each RM tool

Practice-related questions and, Self-declared behavior

- 1. Patient counseling
- 2. Discussing risks with patients
- 3. Liver function monitoring
- 4. Dermatological evaluation
- 5. Treatment discontinuation recommendations

Other variables

- 1. Requesting extra RM tools
- 2. Number of patients treated with voriconazole in the past 12 months
- 3. Downloading the tools from website

9.4. Data Sources

A structured self-administered questionnaire comprised of closed-ended- questions or statements with multiple response choices (ie, questions or statements asking the HCPs to choose from a defined list of responses) will be used to collect the survey data. The questionnaire will collect data on HCP characteristics and their responses to the risk knowledge questions. The data collected from the surveys will be used to inform the evaluation of the effectiveness of the aRMMs.

The questionnaire will begin with a screening module with questions to confirm eligibility. Depending on the answers to the screening questions, survey participation could either be terminated or continued. If ineligible, the respondent is immediately notified with a "thank you" message that survey participation has ended. If eligible, the respondent is allowed to continue survey participation.

Screening questions for the HCPs:

- Consent to participate. Q1
- Whether the HCP managed patient(s) treated with voriconazole during the last 12 months period preceding the survey. Q2
- Employment by Pfizer or any research organization/vendor contracted by Pfizer to administer the survey. Q3
- Participation in qualitative research of the VFEND (voriconazole) RM materials. Q4

Data on HCP demographic characteristics:

- Location (city). Q5a
- HCP medical specialty type (eg, infectious disease physician, pharmacist). Q5
- Number of years practicing medicine. Q6
- Number of self-reported voriconazole-treated patients the HCP managed in the last 12-months period preceding the survey. Q13

Data pertaining to evaluation of the effectiveness of the aRMMs:

The questionnaire includes questions/statements that will assess the risk knowledge of the HCPs. The knowledge level analysed using descriptive statistics and confidence intervals (CIs), will be showcased as the effectiveness of the aRMMs: No formal statistical test will be conducted to test the effectiveness.

- Awareness of each of the RM tools among the HCPs:
 - Receipt of each of the RM tools. Q9, Q10, Q11
 - Review (read) each of the RM tools. Q9.1, Q10.1, Q11.1
- Downloading the tools from website. Q12 (complementary question)
- Requesting additional copies of the VFEND (voriconazole) RM tools. Q23 (complementary question)
- Utilization of the tools in clinical practice. Q14, Q15 and Q16
- Assessing the usefulness of each tool Q17 (complementary question)
- Knowledge/ comprehension of the risks of phototoxicity, SCC of the skin and hepatic toxicity. Q7 and Q8

• Practice-related questions and self-declared behavior with respect to mitigating the risks, as described in the SPC. Q18, Q18a, Q19, Q20, Q21, and Q22

The key messages informing HCPs about the risks of phototoxicity, SCC of the skin and hepatic toxicity with voriconazole, and instructions on how to manage these risks when treating patients with voriconazole have been identified from the most current version of the SPC¹ and will be used for evaluation of the HCP's knowledge.

9.4.1. Data Collection Process

Eligible HCPs (those HCPs to whom the RM tools were distributed by hand) will receive a letter by E-mail inviting them to participate in the survey. The invitation letter will include: an overview of the rationale for the survey, reminder about the educational materials, the secure URL to be copied and pasted into their browser, and a unique user identifier (ID). The survey data collection will be open until 10 completed surveys are received, up to 60-90 days. The survey start date begins within 12-18 months after initiation of distribution (05 February 2023) of the aRMMs tools in the Saudi Arabia.

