9.1. Study design

This is a non-interventional, cross-sectional study to evaluate the effectiveness of RM tools for voriconazole. The study objectives will be accomplished by means of a cross-sectional, web-based survey of all HCPs who were targeted to receive the aRMMs and self-report as prescribers of voriconazole within 12 months preceding the survey in Saudi Arabia (Central, East and North regions). The study aims to obtain completed surveys from 10 HCPs. Data will be collected until 10 completed surveys are obtained or up to a data collection period of 60 to 90 days as a maximum. The data from the HCPs will be collected using a structured self-administered questionnaire to gather evaluation metrics related to the utilization and understanding of RM tool content and messages. In addition, the survey will assess behaviors, including a set of hypothetical scenarios for HCPs. The survey is not intended to be a mechanism for collecting adverse events (AEs), nor is it intended to result in minimizing the numbers of AEs reported. HCPs will be invited by e-mail to participate in the survey and asked to complete the online questionnaire.

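### Section 9.4.1 invites only HCPs who were handed the tools, while the rest of the protocol surveys all HCPs targeted for them; if the two groups differ, acknowledged receipt is biased upward

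*Protocol*

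**What the plan says.** Most of the protocol defines the population by targeting:

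- Section 9.1 describes a "web-based survey of all HCPs who were targeted to receive the aRMMs and self-report as prescribers" of voriconazole.
- Section 9.2 states: "The target population will include all HCPs who were targeted to receive Vfend® aRMM materials within 12 months preceding the survey".
- Section 9.5 says that those to be invited are "All HCPs who were targeted to receive the RM tools (per Pfizer Inc.'s Distribution List.) within the 12 months preceding" the start of the survey.
- The abstract (Annex 1.1, under Study Design, Population and Study Size) repeats these definitions.

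The endpoints use the same denominator. Endpoint 1 in section 9.1.1 is "The proportion of targeted HCPs who acknowledge receiving each of the RM tools", and section 9.7 again refers to targeted HCPs for all four endpoints.

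Section 9.4.1 differs: "Eligible HCPs (those HCPs to whom the RM tools were distributed by hand) will receive a letter by E-mail inviting them". Having been handed the tools is not among the inclusion criteria (9.2.1), the exclusion criteria (9.2.2) or the screening questions (Q1 to Q4).

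One phrase in section 9.2 may link the two definitions. It speaks of HCPs "of these targeted to receive the RM tools in-person, per Pfizer Inc.'s Distribution List".

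**The concern.** An HCP can be on a distribution list without having been handed the materials. Under 9.5 such an HCP is invited and counts in the denominator. Under 9.4.1 the same HCP is never contacted.

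Endpoint 1 asks whether the tools were received. If completed delivery is a condition of being invited, a delivery failure cannot show up in the answer. What remains is mainly whether known recipients remember, yet the result would be reported as a proportion of targeted HCPs and compared with the 80% threshold in Annex 1.5.

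The effect reaches endpoint 2. In the questionnaire, an HCP who answers no or does not remember on receipt skips the reading question for that tool, and Annex 1.5 counts utilisation as successful only if all three tools were read and used. Non-receipt therefore counts as failure on utilisation too.

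Nothing else in the protocol would reveal the loss. The response and refusal rates in 9.7 are built from contacted HCPs only. Section 9.9.2 discusses volunteer bias, non-response and recall but not selection on delivery, and the only direction it gives for receipt is underestimation.

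**Working it through.** **The plan's own figure.** The sample size of 10 is called empirical and has no formula behind it, so there is nothing to reproduce. The awareness criterion is at least 80% of HCPs acknowledging all three tools, which is 0.80 × 10 = 8 of 10.

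**Direction of the bias.** Let c be the share of targeted HCPs who were handed the tools, q the probability that such an HCP acknowledges all three, and u the same probability for a targeted HCP who was not handed them.

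- Proportion among all targeted HCPs: c·q + (1 − c)·u
- Proportion under 9.4.1: q
- Difference: q − [c·q + (1 − c)·u] = (1 − c)(q − u)

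The difference is zero if delivery was complete (c = 1) or if HCPs who were not handed the tools acknowledge them just as often (u = q). It is positive whenever c < 1 and u < q. The documents give no value for c, q or u.

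**Sensitivity under assumed inputs.** Take u = 0 and recall r per tool. Then q = r³ if recall is independent across tools, and q = r if it is fully correlated. With p = c·q, the chance of meeting the criterion is P(X ≥ 8), where X is binomial(10, p). Each cell runs from independent to correlated recall.

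| Recall per tool, r | All invited were handed the tools (c = 1) | 80% of those targeted were (c = 0.8) |
|---|---|---|
| 0.80 | 0.06 to 0.68 | 0.01 to 0.24 |
| 0.90 | 0.46 to 0.93 | 0.14 to 0.44 |
| 0.95 | 0.84 to 0.99 | 0.35 to 0.56 |
| 1.00 | 1.00 | 0.68 |

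Example for r = 0.95 with independent recall: 0.95³ = 0.857. At c = 1, p = 0.857 and P = 0.84. At c = 0.8, p = 0.8 × 0.857 = 0.686 and P = 0.35.

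The table shows how sensitive the result could be; it does not estimate the bias in this study. Setting u = 0 exaggerates the contrast, because Q9 to Q11 ask whether the respondent or the hospital received the tools, and an HCP missed by hand delivery may truthfully answer yes. The binomial also treats the respondents as a random draw, whereas they are volunteers from a small pool.

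**The case against.** The strongest reply is that the two wordings describe one list. Section 9.2 speaks of in-person targeting under the Distribution List, and in-person delivery is hand distribution. The abstract says distribution ran until 05 February 2024, before the protocol date, which would explain the past tense in 9.4.1. No section mentions a failed delivery, and the counts that might settle the matter are not visible. This stands as a possibility: it is not established that the groups differ. It does not remove the conflict, because section 9.2 still says targeted and no section says that every targeted HCP was handed the tools.

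Three stronger readings are tempting, and the documents do not support them.

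- *Under 9.4.1 the receipt endpoint is almost certain to succeed.* Success is acknowledged receipt of all three tools; no and do-not-remember answers count as failures, and section 9.9.2 expects recall to lower the figure. Even with full delivery, the chance of passing is 0.46 to 0.93 at 0.90 recall per tool. A 95% chance needs p of about 0.91, or about 0.97 recall per tool if recall is independent.
- *The programme's verdict would flip from fail to pass.* Assuming q = 0.9 and u = 0.1, awareness among targeted HCPs is 0.1 + 0.8c, or 74% at c = 0.8, against 90% under 9.4.1. Those inputs are invented, and with 10 respondents a true 74% still meets the criterion about half the time.
- *Section 9.4.1 governs the invitations.* No section gives it precedence. Section 9.2 also sets out a recruitment process, and 9.5 says that all targeted HCPs will be invited.

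**Conclusion.** The conflict is in the text and should be reconciled. Section 9.4.1 adds a delivery condition that the other population definitions, the eligibility criteria and the endpoint denominators do not contain.

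Whether it does harm depends on a fact the protocol does not state. If every targeted HCP was handed the tools, this is a wording inconsistency only. If some were not, following 9.4.1 biases acknowledged receipt upward as a measure of programme reach, carries that bias into reading and utilisation, and leaves endpoint 1 measuring mainly recall. The direction assumes only that HCPs who were not handed the tools acknowledge them less often than those who were. The documents do not allow the size to be derived.

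**What to change.** In 9.4.1, replace the parenthesis with: *all HCPs on the Distribution List who were targeted to receive the RM tools, whether or not hand delivery was completed*. This agrees with 9.5. Report endpoint 1 on that frame.

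If the distribution records hold delivery status, which the protocol does not say, report descriptively how many targeted HCPs had documented delivery. That count can be taken from the list itself, without linking identities to survey answers. A formal split of about 10 respondents by delivery status is not needed and would tell little; section 9.9.2 already warns that the sample may not support subgroups.

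The cost is one sentence, plus one count if the records allow it. The sample size, questionnaire and timeline do not change. The downside for the sponsor is that the awareness figure may be less favourable.
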